### 8.3. Study population with inclusion and exclusion criteria

#### *Objective 1*

##### Inclusion criteria

- Present in the data source during the period of 01/01/2017 to 31/12/2024.

##### Exclusion criteria

- Not applicable for this objective.

#### *Objective 2*

##### Inclusion criteria

- Present in the data source during the period of 01/01/2017 to 31/12/2024.
- Drug prescription or dispensing record of prespecified immunoglobulin brands during the study period.

##### Exclusion criteria

- Not applicable for this objective.

The preliminary code list for immunoglobulins is provided in [ANNEX IV](#).

#### *Objectives 3–4*

##### Inclusion criteria

- Present in the data source during the period of 01/01/2017 to 31/12/2024.
- Minimum 180 days of available history before index data. This criterion does not apply for hospital data source CDW Bordeaux.
- First drug prescription or dispensing record of prespecified immunoglobulin brand during the study period.
- No prior immunoglobulin exposure in the 180 days prior to the index date. This criterion does not apply for hospital data source CDW Bordeaux.

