## 8.2. Follow-up

For prevalence estimations of individuals with recorded immunoglobulin prescriptions among the general study population (*objective 1*), individuals present in the data source between 1st of January 2017 and 31st of December 2024 will be included. For prevalence estimations among immunoglobulin users (*objective 2*), follow up will start on date of immunoglobulin prescription during the study period.

For patient-level drug utilisation (*objective 3*) and characterisation of individuals initiating immunoglobulin treatment (*objective 4*), follow-up of incident immunoglobulin users will start on the date of the first immunoglobulin prescription record of prespecified immunoglobulin brands during the study period. For primary care data sources, individuals are required to have 180 days data visibility prior to study inclusion and should not have a record of immunoglobulin prescription in the 180 days prior to study inclusion. For hospital care data settings, individuals are not required to have prior data availability, and no washout period will be applied prior to study inclusion. To ensure sufficient follow-up (*objectives 3–4*), only individuals with a first record of immunoglobulin prescription at least 180 days before the end of data availability in each data source will be included.

Follow-up (*objectives 1–4*) will end on the earliest of i) loss to follow-up, ii) death, iii) end of observation period (the latest available data), iv) or study end date 31/12/2024, whichever occurs first.

The code lists used to identify the start and end of follow-up determining events are presented in [Annex IV](#).

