##### Exclusion criteria

- Individuals with a first immunoglobulin record <180 days prior to the end of data availability in the respective data source (to ensure sufficient follow-up).

The preliminary code list for immunoglobulins brands is provided in [ANNEX IV](#).

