## 8.5. Study period

The study period is from 01/01/2017 to 31/12/2024. The data availability of the included data sources aligns with the study period.

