The number of prescriptions, initial and cumulative dose of the index drug, as well as duration of use, will be provided per prespecified immunoglobulin brand as minimum, q25, median, q75, and maximum. For data sources where duration cannot be calculated, due to e.g., missing information on quantity or dosing, treatment duration will not be provided.

### Objective 4

Characteristics of individuals will be assessed in predefined time windows around the date of the first recorded prescription of immunoglobulins (index date) during the study period. For primary care data sources, a washout period of 180 days will be applied. Characteristics will be described for each prespecified immunoglobulin brand by means of large-scale characterisation and prespecified patient-level characteristics based on OMOP CDM mapped data using the *CohortCharacteristics* (<https://github.com/darwin-eu/CohortCharacteristics>) and *DrugUtilisation* (<https://github.com/darwin-eu/DrugUtilisation>) R packages, developed by DARWIN EU®.

Characteristics of interest will be reported as counts and proportions for categorical variables and as minimum, q25, median, q75, and maximum for continuous variables. Demographic characteristics, including age and sex, will be assessed at the date of first recorded prescription of immunoglobulins (index date) during the study period. Characterisation of prespecified indications for use will be assessed any time prior to 7 days after the index date, 30 days prior to 7 days after the index date, and 7 days prior to 7 days after the index date. Large-scale characterisation of comorbidities prior to immunoglobulin treatment will be assessed 30 days prior to the index date, 1 year prior to the index date, and any time prior to the index date. Characterisation of prespecified common infections and prespecified antibiotics treatment among immunoglobulin initiators will be assessed up to 30 days post-index and up to 365 days post-index.

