#### **United Kingdom: Clinical Practice Research Datalink GOLD (CPRD GOLD)**

CPRD GOLD will be included in this study because it is a primary care data source that provides relevant information on the use of immunoglobulins in the general population.

Based on a preliminary feasibility assessment, the expected number of person counts for immunoglobulin use in CPRD GOLD will be 73,600.

Moreover, data availability and follow-up in CPRD GOLD is sufficient, as data availability starts in 1987, and the date of most recent data extraction is 05/2025, which aligns with the study period. The median follow-up of the first observation period is 2,150 days.

There are no study specific limitations present in CPRD GOLD.

Lastly, CPRD GOLD has blanket approval, which makes the execution of this study feasible within the current study timelines.

Table S1. Fitness-for-use assessment of data sources.

Design elements	Operational definition	Data elements for valid capture	Criticality of the quality of the element, including justification where relevant	Suggested extensiveness assessment	Suggested assessment of other quality dimensions	Suggested substantiation by documentation
Study population	General study population ( obj. 1 )	N/A	N/A	N/A	N/A	N/A
	Population with an immunoglobulin prescription ( obj. 2–4 )	Prescription of immunoglobulin treatment (RxNorm code)	High	100% will have an immunoglobulin prescription, the expected number of persons counts for immunoglobulins in the data sources included in this study range from 10,900 (CDW Bordeaux) to 73,600 (CPRD GOLD).	100% of prescriptions have been mapped to RxNorm	N/A
Treatment/exposure	Immunoglobulin prescription	Prescription of immunoglobulin treatment (RxNorm code)	High	N/A (to be assessed on a research question basis)	N/A	N/A
Comparator group (not relevant)	N/A	N/A	N/A	N/A	N/A	N/A
Key outcomes per objective	Immunoglobulin prescription ( obj. 1 )	Prescription of prespecified immunoglobulin treatment (RxNorm code), including, if available, route of administration	Medium	Immunoglobulin prescriptions are included in all data sources. The expected number of persons counts for immunoglobulins in the data sources included in this study range from 10,900 (CDW Bordeaux) to 73,600 (CPRD GOLD).	N/A	N/A

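### In the two primary care sources, returning users can enter the 'initiator' cohort of objectives 3–4: earlier immunoglobulin use is checked for only 180 days, and the look-back implied by 'first' depends on index date

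*Protocol*

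**What the plan says.** Section 8.5 sets the clock: "The study period is from 01/01/2017 to 31/12/2024". Section 8.3 (objectives 3–4) defines the index event as "First drug prescription or dispensing record of prespecified immunoglobulin brand during the study period". For the primary care sources it adds "Minimum 180 days of available history before index data" and "No prior immunoglobulin exposure in the 180 days prior to the index date". Neither addition applies to CDW Bordeaux. Section 8.3 also excludes "Individuals with a first immunoglobulin record <180 days prior to the end of data availability in the respective data source".

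Section 8.2 describes the resulting people as incident: "follow-up of incident immunoglobulin users will start on the date of the first immunoglobulin prescription record of prespecified immunoglobulin brands during the study period". Section 8.6.1 and the drug exposure text in Section 8.8.3 use the same brand-based rule with the 180-day washout. The objective 4 text in Section 8.8.3 words the index differently, as the "date of the first recorded prescription of immunoglobulins (index date) during the study period", and names no brand.

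Table 1 gives data from 1989 for IQVIA DA Germany and from 1987 for CPRD GOLD. Section 9 says that true incident status is uncertain, but only for CDW Bordeaux.

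**The concern.** Two conditions act together, and they look back over different spans. The washout covers any immunoglobulin for a fixed 180 days. The word 'first' covers brand records back to 01/01/2017 and no further. How clean an initiator is therefore depends on the index date, and early index dates are the ones most open to people who are resuming treatment.

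Several outputs assume a true start. Initial dose in Table 3 is not an initial dose in a returning user. The short indication windows, [-30, +7] and [-7, +7], can miss a diagnosis that was coded when treatment first began. The 30-day and 365-day infection and antibiotic windows combine newly treated and previously treated people.

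No table for objectives 3–4 is split by index year or by earlier use, so a reader of the report could not detect the mixture. Since Section 9 raises the issue for the hospital source alone, the primary care cohorts will be taken as clean.

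**Working it through.** The protocol states no effective washout, so there is no figure to reproduce. The check is date arithmetic on its rules.

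**Inputs.** Study period 01/01/2017 to 31/12/2024 (Section 8.5). Washout and minimum history of 180 days, and exclusion of first records less than 180 days before the end of data (Section 8.3). Data end 12/2024 for IQVIA DA Germany and 05/2025 for CPRD GOLD (Table 1). Median first observation period 116 days for IQVIA DA Germany (Annex II); for CPRD GOLD, "The median follow-up of the first observation period is 2,150 days". Assumption: a month-only data end means the last day of that month.

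**Step 1: latest possible index.** Latest index = the earlier of 31/12/2024 and the end of data minus 180 days.
- IQVIA DA Germany: 31/12/2024 − 180 days = 04/07/2024.
- CPRD GOLD: 31/05/2025 − 180 days = 02/12/2024.

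**Step 2: implied brand-free look-back.** With 'first' taken over the study period, look-back at index date t = max(180, t − 01/01/2017) days. The second term reaches 180 on 30/06/2017 and dominates after that.

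| Index year | Maximum look-back (days) |
|---|---|
| 2017 | 180–364 |
| 2018 | 365–729 |
| 2019 | 730–1,094 |
| 2020 | 1,095–1,460 |
| 2021 | 1,461–1,825 |
| 2022 | 1,826–2,190 |
| 2023 | 2,191–2,555 |
| 2024, IQVIA DA Germany | 2,556–2,741 |
| 2024, CPRD GOLD | 2,556–2,892 |

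The ceilings are 2,741/365.25 = 7.5 years and 2,892/365.25 = 7.9 years. Taking the first day of the month as the data end lowers them to 2,711 and 2,862 days (7.4 and 7.8 years).

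**Step 3: cap by observed time.** With O days observed before index (at least 180), look-back = min(O, max(180, t − 01/01/2017)). For an index on 1 July of 2017, 2018, …, 2024:
- O = 180: 180 in every year.
- O = 365: 181, then 365 from 2018 on.
- O = 2,150: 181, 546, 911, 1,277, 1,642, 2,007, 2,150, 2,150.

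The median first observation period in IQVIA DA Germany (116 days, 0.3 years) is below the 180-day entry requirement, so growth there is probably much smaller than in CPRD GOLD (2,150 days, 5.9 years).

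**Step 4: what this does to individuals.** A record on 15/06/2016 followed by one on 15/03/2017 leaves a gap of 273 days. The washout is passed, the 2017 record is the first in the period, and the person enters as an initiator in 2017. With records of the same brand on 15/06/2021 and 15/03/2023 (638 days apart), the 2023 record is not the first in the period and cannot be an index. The longer gap fails and the shorter one passes.

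**Step 5: what the longer look-back does not cover.** Only records that define 'first' are affected. Any other immunoglobulin record is screened for 180 days in every year. If 'first' is per brand, a 2024 initiator may have used another brand in 2020.

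**Step 6: size.** The share of returning users needs a restart rate, which the protocol does not give. As an illustration, take a constant number of new starts, restarts at r per year and D years observed after the first start. The ratio of returning to new users at t years after 01/01/2017 is then q = r·exp(−r·t)·(D − t), and their share is q/(1 + q). At mid-2017 (t = 0.5):
- r = 0.02, D = 3: q = 0.02 × 0.990 × 2.5 = 0.050, share 5%.
- r = 0.20, D = 8: q = 0.20 × 0.905 × 7.5 = 1.357, share 58%.

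Both r and D are assumed. The spread shows that the size is unknown.

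**The case against.** The strongest reply is that the rule is stated openly, that a 180-day washout is a recognised choice in a descriptive study without hypothesis tests, and that moving to first-ever use would change the target population. Database start years are not personal histories: IQVIA DA Germany has no linkage between practices, and a CPRD GOLD patient can receive a new identifier on changing practice (Annex I). Searching all history would still leave a look-back that varies between people. All of this stands. It tells against redefining the cohort, but not against showing who in it has an earlier visible record.

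A reader might also infer more than the documents support:
- **An effective washout of about 8 years in 2024.** The 2,921 days to 31/12/2024 is not an eligible index in either source, and the attainable values are ceilings limited by observed time.
- **Brands that appear later have purer initiators.** This needs 'first' to be fixed, which it is not: Sections 8.2, 8.3 and the drug exposure text name brands, while the objective 4 text says immunoglobulins. On a per-brand reading, users of a newer brand may have switched from another more than 180 days earlier. The protocol gives no launch dates.
- **A spurious fall in initiators over calendar time.** No planned output shows initiators by year. Tables 3–8 pool index years, and the trend figures belong to objectives 1–2.
- **A share of returning users that starts high and falls to zero.** The share rests on assumed restart rates, and the zero comes from the cut-off at D in the formula.

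Finally, if 'first' were applied only after the washout, the guaranteed look-back would be 180 days in every year. Sections 8.3 and 8.6.1 read more naturally the other way, but the Table 2 shell has no first-record step to settle it. On that order, earlier users could enter in any year, so the mixture remains.

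**Conclusion.** The point holds as a matter of definition and reporting. In IQVIA DA Germany and CPRD GOLD, the people called incident are an unquantified mix of new and returning users. On the more natural reading, the brand-free look-back runs from 180 days up to mid-2017 to at most about 7.5 and 7.9 years respectively, less where personal observation is shorter. Other immunoglobulins are screened for 180 days throughout.

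The consequence is a mixed population behind initial dose, the short indication windows and the post-index infection and antibiotic results; no reported time trend is distorted. The share of returning users cannot be derived from the protocol, and any effect on comparisons between brands depends on a reading that the text leaves open. It merits an amendment because the protocol already reads all prior history for indications and comorbidities in these same people, yet does not use it for earlier immunoglobulin records.

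**What to change.** In Sections 8.2, 8.3, 8.6.1 and 8.8.3, keep the 180-day minimum history and washout for entry, and:

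1. State whether 'first' is per brand or across all prespecified brands, and whether it is applied before or after the washout. Align the objective 4 wording with this and add the step to Table 2.
2. For IQVIA DA Germany and CPRD GOLD, search all available history before index, including before 01/01/2017, for any immunoglobulin record.
3. Add to Tables 2 and 4 the number and share of initiators with such a record.
4. Report Tables 3–8 also restricted to initiators without one.
5. Extend the Section 9 limitation on incident status to the two primary care sources.

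The cost is one further look-back query, a few rows and a repeated set of tables, with no new data. Cells for rare brands will be smaller, and more will fall under the minimum count of 5. Look-back will still differ between people, but Table 4 already reports prior observation, so readers can judge this.

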##### Exclusion criteria

- Individuals with a first immunoglobulin record <180 days prior to the end of data availability in the respective data source (to ensure sufficient follow-up).

The preliminary code list for immunoglobulins brands is provided in [ANNEX IV](#).

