  - Hepatology, including:
    - Hepatitis A
  - Other indications, which will be assessed overall and separately for each indication, where available, including:
    - Oncology
    - Autoimmune or paraneoplastic encephalitis
    - Epilepsy

- Progressive systemic sclerosis
  - Sjögren syndrome
  - COVID-19
  - Alzheimer
- Comorbidities: The top 10 most frequent diagnostic codes (comorbidities) will be identified through large-scale characterisation. These will be assessed 30 days prior to the index date [-30, 0], 1 year prior to the index date [-365, 0], and any time prior the index date [-inf, 0].

Common infections: Prespecified common infections among individuals initiating treatment with prespecified immunoglobulin brands will be assessed up to 30 days post-index [0, +30] and up to 365 days post-index [0, +365]. The following types of infections [4] will be assessed:

- Systemic infections, including:
  - Gram negative sepsis
  - Bacteraemia
- Bacterial infections, including:
  - Bacterial infectious disease
- Central nervous system infections, including:
  - Meningitis
- Respiratory & ear, nose, throat, ocular infections, including:
  - Otitis
  - Conjunctivitis
  - Bronchitis
  - Sinusitis
  - Respiratory tract infections
- Fungal infections, including:
  - Opportunistic mycosis
  - Invasive fungal infection
- Gastrointestinal & intra-abdominal infections, including:
  - Acute diarrhoea
  - Gastrointestinal infections
  - Peritonitis
- Urinary infections, including:
  - Urinary tract infections
- Viral infections:
  - Chronic enteroviral infections
  - Herpesvirus infections

- Antibiotic treatment: Exposure to prespecified antibiotics will be assessed up to 30 days post-index [0, +30] and up to 365 days post-index [0, +365]. The following classes of antibiotic ingredients will be assessed:
  - Tetracyclines
  - Amphenicols
  - Beta-lactam antibacterials, penicillins
  - Other beta-lactam antibacterials
  - Sulphonamides and trimethoprim
  - Macrolides, lincosamides, and streptogramins
  - Aminoglycoside antibacterials
  - Quinolone antibacterials
  - Other antibacterials

The preliminary concept sets used for the identification of covariates are described in [Annex IV](#). Final concept sets will be defined following input from EMA.

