## ANNEX II. Fitness for use assessment

### Data source justification for inclusion and key characteristics

#### **France: Clinical Data Warehouse of Bordeaux University Hospital (CDW Bordeaux)**

CDW Bordeaux will be included in this study because it is a hospital data source that provides relevant information on the use of immunoglobulins in the general population.

Based on a preliminary feasibility assessment, the expected number of person counts for immunoglobulin use in CDW Bordeaux will be 10,900.

Moreover, data availability and follow-up in CDW Bordeaux is sufficient, as data availability starts in 2005, and the date of most recent data extraction is 09/2025, which aligns with the study period. The median follow-up of the first observation period is 247 days.

There are no study specific limitations present in CDW Bordeaux.

Lastly, IRB approval for CDW Bordeaux is estimated to take 1 to 2 weeks, which makes the execution of this study feasible within the current study timelines.

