#### **Germany: IQVIA Disease Analyzer Germany (IQVIA DA Germany)**

IQVIA DA Germany will be included in this study because it is a primary care data source that provides relevant information on the use of immunoglobulins in the general population.

Based on a preliminary feasibility assessment, the expected number of person counts for immunoglobulin use in IQVIA DA Germany will be 47,500.

Moreover, data availability and follow-up in IQVIA DA Germany is sufficient, as data availability starts in 1989, and the date of most recent data extraction 12/2024, which aligns with the study period. The median follow-up of the first observation period is 116 days.

There are no study specific limitations present in IQVIA DA Germany.

Lastly, IQVIA DA Germany requires no IRB approval, which makes the execution of this study feasible within the current study timelines.

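### The 180-day follow-up rule is anchored to end of data while follow-up stops at 31/12/2024, so it fails in CDW Bordeaux and CPRD GOLD, and in every source 180 days is too short for the 365-day proportions

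*Protocol*

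**What the plan says.** The exclusion criterion for objectives 3–4 (section 8.3) removes "Individuals with a first immunoglobulin record <180 days prior to the end of data availability in the respective data source". Section 8.2 repeats the requirement, asking for a first record "at least 180 days before the end of data availability in each data source", and the abstract does the same. The stated purpose is sufficient follow-up, and mock Table 2 in section 8.8.4 has an attrition row for 180 days of potential follow-up.

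Section 8.2 then lists the events that end follow-up for objectives 1–4. The last is "or study end date 31/12/2024, whichever occurs first". Note d to Figure 2 says the same for objectives 3–4. Section 8.5 fixes the dates: "The study period is from 01/01/2017 to 31/12/2024".

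The sources do not end together. For CDW Bordeaux, Annex II states that "data availability starts in 2005, and the date of most recent data extraction is 09/2025". Table 1 and Annex II give 05/2025 for CPRD GOLD and 12/2024 for IQVIA DA Germany.

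Section 8.6.3 says that common infections "will be assessed up to 30 days post-index [0, +30] and up to 365 days post-index [0, +365" (the closing bracket follows), and sets the same two windows for antibiotics. Mock Tables 7 and 8 report both windows as counts and percentages by brand and source. The protocol states no restricted denominator, minimum observed time or censoring rule for them.

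**The concern.** A rule that guarantees follow-up has to be measured back from the date on which follow-up can actually stop. Here it is measured from the end of the data, which in two of three sources falls five to nine months after the study end date that closes follow-up. People admitted near the end of 2024 then have less than the promised 180 days, and the attrition row would describe them wrongly.

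Separately, even a rule that works gives only 180 days, while the longer window is 365 days. An initiator who cannot be followed for a year but is counted in a one-year percentage lowers it. The sources lose different amounts, and Tables 7 and 8 set them side by side. Post-index infections and antibiotics are a stated part of objective 4.

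**Working it through.** **Inputs.** Study period 01/01/2017 to 31/12/2024, which is 2,922 possible index dates (8.5). End of follow-up no later than 31/12/2024 (8.2). End of data 09/2025, 12/2024 and 05/2025 (Table 1, Annex II). The day of the month is not given, so the first and last days of each month are used as a range.

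**Formulas.** Last admissible index date = the earlier of (end of data − 180 days) and 31/12/2024. Minimum calendar follow-up = the earlier of (31/12/2024, end of data) − last admissible index date.

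**Step 1: does the rule deliver its own 180 days?**

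| Source | End of data − 180 days | Last index date | Minimum follow-up |
|---|---|---|---|
| IQVIA DA Germany | 04/06 to 04/07/2024 | 04/06 to 04/07/2024 | 180 days |
| CPRD GOLD | 02/11 to 02/12/2024 | 02/11 to 02/12/2024 | 59 to 29 days |
| CDW Bordeaux | 05/03 to 03/04/2025 | 31/12/2024 | 0 days |

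The 180 days are reproduced only for DA Germany. In CDW Bordeaux the cut-off falls after the study period, so the rule removes no one.

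**Step 2: share of admitted index dates with short calendar follow-up.** Uniform entry over the admissible dates is assumed.

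| Source | Admitted dates | <30 days | <180 days | <365 days |
|---|---|---|---|---|
| CDW Bordeaux | 2,922 | 30 (1.0%) | 180 (6.2%) | 365 (12.5%) |
| CPRD GOLD | 2,863 to 2,893 | 0 to 1 (0.0%) | 121 to 151 (4.2–5.2%) | 306 to 336 (10.7–11.6%) |
| IQVIA DA Germany | 2,712 to 2,742 | 0 | 0 | 185 (6.7–6.8%) |

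**Step 3: effect on a one-year proportion.** Assume a constant hazard h = −ln(1 − r)/365 for a true one-year risk r, with every initiator in the denominator. The expected crude proportion is the average over admitted index dates of 1 − exp(−h × min(365, calendar follow-up)). For r = 40%:

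- CDW Bordeaux: 37.7%
- CPRD GOLD: 38.1–38.4%
- IQVIA DA Germany: 39.4%

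For CDW Bordeaux, true risks of 20% and 60% would appear as 18.8% and 56.8%.

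**Step 4: the two possible repairs.**

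- *Re-anchor to the earlier of end of data and 31/12/2024.* The last index date becomes 04/07/2024 (04/06/2024 if the German data end on 01/12/2024), and the minimum is 180 days everywhere. Of 2,742 admitted dates, 185 (6.7%) still fall short of 365 days. A complete 365-day window needs an index date by 01/01/2024, which keeps 2,557 of 2,922 dates (87.5%).
- *Let the post-index windows run to end of data.* The rule as written then gives at least 180 days. Admitted dates with under 365 days fall to 92–121 of 2,922 (3.1–4.1%) in CDW Bordeaux and 185 of 2,863–2,893 (6.4–6.5%) in CPRD GOLD. DA Germany is unchanged.

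**The case against.** **Small effect.** From the calendar alone, a true 40% moves by at most about 2.3 points (40 − 37.7), and the sources differ by under 2 points (39.4 − 37.7). The 30-day window is essentially intact: about 1.0% of Bordeaux dates are affected and practically none elsewhere. Zero follow-up from the anchor arises only in CDW Bordeaux, and DA Germany has no anchor mismatch. All of this stands and sets the severity.

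**Descriptive study, with disclosure.** No hypothesis is tested, sources are not pooled, and mock Table 4 reports future observation by brand and source. That would let a reader see short follow-up, but it neither corrects the percentages nor makes the attrition row true.

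**Left to a SAP.** How incompletely observed people enter the denominator may be settled there, so counting them as event-free is an inference. This is fair for the denominator. It does not cover the anchor, the end of follow-up or the windows, which the protocol fixes and which do not fit together.

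**A stronger reading.** A reader might note that for DA Germany "The median follow-up of the first observation period is 116 days", and that the figure for CDW Bordeaux is 247 days. They might infer that most initiators cannot be seen for a year and that country differences would mainly reflect length of observation. The documents do not support this. The medians describe first observation periods in the whole source, not time after immunoglobulin initiation. In DA Germany and CPRD GOLD initiators must already have 180 days of history, which exceeds the German median before follow-up begins. Any figure derived from these medians depends heavily on the assumed distribution. Section 9 does say that observation ends at the last event (DA Germany) or last visit (CDW Bordeaux), so further loss is plausible, but its size among initiators is not established.

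**Day 0.** A reader might also object that the post-index windows include the index date. They are openly written that way in section 8.6.3 and in Tables 7 and 8, and no causal sequence is claimed. This is a preference, not an error.

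**Conclusion.** The rule as written does not do what it says it is for. It secures 180 days of potential follow-up in IQVIA DA Germany, about 29–59 days at minimum in CPRD GOLD, and none in CDW Bordeaux. In every source it is too short for the 365-day window: about 12.5%, 11–12% and 7% of admitted index dates (CDW Bordeaux, CPRD GOLD, DA Germany) lack a full calendar year. The resulting bias in the 365-day proportions is downward, modest and different by source.

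The date arithmetic rests only on the documents and the unknown day of the month. The shares also assume uniform entry. The bias figures further assume a constant hazard and all initiators in the denominator. If the programmed windows in fact use data after 31/12/2024, the 180-day shortfall closes in CDW Bordeaux and CPRD GOLD, but section 8.2 then misstates the end of follow-up. Either way the sections must be reconciled. Severity: should be fixed.

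**What to change.** 1. Reconcile sections 8.2 and 8.3, the abstract and Figure 2 note d. Either anchor the 180-day rule to the earlier of end of data and 31/12/2024, or let the post-index windows for infections and antibiotics run to each source's end of data.
2. In Tables 7 and 8, restrict the 365-day denominators to initiators with at least 365 days of potential (administrative) follow-up, and state this in section 8.6.3 or 8.8.3.
3. Beside each percentage, report the number actually observed through day 30 and day 365. This shows any person-level loss that the calendar rule cannot prevent.
4. A censored cumulative incidence may be added as a sensitivity analysis. It should not be mandatory: where observation ends at the last event or visit, censoring is tied to care-seeking and independent censoring is doubtful.

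Cost: a few sentences and one extra count per cell. Under uniform entry, about 7–12% of currently admitted initiators drop out of the 365-day results. Re-anchoring also removes some of these from the whole objectives 3–4 cohort: 180 of 2,922 index dates (6.2%) in CDW Bordeaux and 4.2–5.2% in CPRD GOLD. Running the windows to end of data avoids that and cuts the 365-day loss to about 3–4% in CDW Bordeaux and 6.5% in CPRD GOLD.
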